### **5.6.2.      Laboratory, Vital Signs, and Physical Examination**

For laboratory safety parameters and vital signs, only abnormalities emerging after vaccination will be tabulated by worst abnormality grade using the FDA table in Protocol Appendix 5.

Vital signs including temperature, pulse/heart rate, respiratory rate, and blood pressure (systolic and diastolic) will be summarized over time, using descriptive statistics. Abnormalities emerging after vaccination will be tabulated by worst abnormality grade using the FDA table in Protocol Appendix 5.

An abnormality (toxicity grade or abnormality based on normal ranges) will be considered as emerging in a particular period if it is worse than the baseline value. If the baseline is missing, the abnormality is always considered emerging. A shift from ‘abnormally low’ at baseline to ‘abnormally high’ post baseline (or vice versa) is also emerging. In case a laboratory test result is censored (no numeric value is available, but only a verbatim term) then a numeric value will be imputed by a value exceeding the cut-off value with one unit. (<x: subtract 1 unit from x, >x: add 1 unit to x; eg <3.45 is imputed with 3.44).

In case no toxicity grades are defined for a test, the abnormalities (above/below normal range) will be used. In determining toxicity grades, the following rules are applied:

- Worst grades/abnormalities are determined over the whole observational period for each trial period separately, including all post-baseline measurements of that period.
- The abnormalities ‘abnormally low’ and ‘abnormally high’ are considered equally important, i.e., if a participant has an abnormally low as well as an abnormally high value post-baseline, both abnormalities are shown in the tables. (This means that the sum of the percentages can be more than 100%)
- Note: as the grading scale for some parameters in the grading table has some gaps (zones where no toxicity grade definition exists), laboratory results falling in these zones will be allocated to the adjacent worst-case grade.
- If a lab value falls within the grading as specified in the grading table but also within the local lab normal limits, the value is considered as normal.

For the grades, no distinction will be made between test results of samples obtained under fasting and under non-fasting conditions: in case limits under fasting and non-fasting conditions differ, the limits of the conditions (fasting/non-fasting) of scheduled visits as planned in the CTP will always be used, also for samples obtained under a different condition (e.g., samples of withdrawal visits).

A listing of participants with fever according to the FDA grading table will also be provided. In addition, temperature measurements (whether obtained from the diary or from on-site assessments) will be allocated to predefined temperature intervals (from 37.5° C until 40°C, in steps of half degree increments; eg <37.5, 37.5-<38, 38-<38.5, ... >40), and the worst temperature reported over the first 7 first days after a vaccination (Day 1 to Day 8, from any of the diary or the on-site assessments) will be tabulated by intervals.

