4.2. Scientific Rationale for Study Design

Dose Selection

The rationale behind the selection of the doses is described in Section 4.3, Justification for Dose.

Regimen Selection

In **Cohort 1**, initial safety and immunogenicity assessment of a 2-dose regimen of INFLUENZA G1 mHA (CCI [REDACTED] with or without Al(OH)₃ adjuvant, will be performed.

In **Cohort 2**, safety and immunogenicity of high-dose (CCI [REDACTED] INFLUENZA G1 mHA (with and without Al(OH)₃ adjuvant) administered in a 2-dose or single-dose regimen will be assessed.

The vaccination regimens are with administration of study vaccination (active or placebo) on Day 1 and Day 57 (8-week interval). The interval is based on data from other studies by the sponsor in which higher antibody responses were observed in studies with an 8-week interval regimen compared to studies with a 4-week interval regimen (Milligan 2016). A longer (eg, 12-week interval) regimen was not considered for the current study because this would be impractical for an influenza vaccine.

Blinding, Control, Study Phase/Periods, Intervention Groups

A placebo control will be used to establish the frequency and magnitude of changes in clinical endpoints that may occur in the absence of active intervention. Randomization will be used to minimize bias in the assignment of participants to intervention groups, to increase the likelihood that known and unknown participant attributes (eg, demographic and baseline characteristics) are evenly balanced across intervention groups, and to enhance the validity of statistical comparisons across intervention groups. Blinded intervention will be used to reduce potential bias during data collection and evaluation of clinical endpoints.

Biomarker Collection and Limited Genetic Testing

It is recognized that genetic variation can be an important contributory factor to interindividual differences in response to vaccination. Limited genetic testing (eg, gene expression profiling) may help to explain interindividual variability in clinical outcomes and may help to identify population subgroups that respond differently to vaccination. The goal of the gene expression profiling component is to collect RNA to allow the identification of genetic factors that may influence the safety, reactogenicity and immunogenicity of INFLUENZA G1 mHA.

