Note: Investigators must ensure that all study enrollment criteria have been met prior to the first vaccination. If a participant's clinical status changes (including any available laboratory results or receipt of additional medical records) after screening but before the first dose of study vaccine is given such that the participant no longer meets all eligibility criteria, then the participant must be excluded from participation in the study. The clinical laboratory results on Day 1 and Day 57 are not required for eligibility assessment. Section 5.4, Screen Failures, describes options for retesting. The required source documentation to support meeting the enrollment criteria are noted in Section 10.3, Appendix 3, Regulatory, Ethical, and Study Oversight Considerations.

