#### 5.1.1. Study Phases

A baseline (or reference) value will be defined as the value of the last available assessment prior to the vaccination on Day 1.

The safety analysis will present all results by phase. Immunogenicity results will be presented per scheduled time point as appropriate. Listings will be shown per phase and time point.

Study day or relative day is defined as follows:

- Study Day = visit date – date of Day 1 + 1; if visit date  $\geq$  date of Day 1 (date of first vaccination).
- Study Day = visit date – date of Day 1; if visit date  $<$  date of Day 1 (date of first vaccination).

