**Table 1: Phase Definitions**

Phase	Phase #	Period	Period #	Interval	
				From	To
Screening	1			Date and time of signing the informed consent form a	One minute prior to start of Post-dose 1 period
Regimen	2	Post-dose 1	1	Date and time of first vaccination	Minimum of: a) 23:59 at the date of last contact (for early discontinuation) b) 23:59 at the date of database cut-off date in case of interim c) 23:59 on 28 days after the first vaccination (23:59 of day of vaccination + 28 days) d) One minute prior to Post-dose 2
Follow-up 1	3	Follow-up 1		One minute after post-Dose 1 period end	Minimum of: a) 23:59 at the date of last contact (for early discontinuation) b) 23:59 at the date of database cut-off date in case of interim c) One minute prior to Post-Dose 2
Regimen	2	Post-dose 2	2	Date and time of second vaccination	Minimum of: a) 23:59 at the date of last contact (for early discontinuation) b) 23:59 at the date of database cut-off date in case of interim c) 23:59 on Day 28 after the second vaccination (23:59 of day of vaccination + 28 days)
Follow-up 2	4	Follow-up 2		One minute after Post-dose 2 period end	Minimum of: a) 23:59 at the date of last contact b) 23:59 at the date of database cut-off date in case of interim

a In case an earlier date is available (e.g., for lab or vital signs), then use the very first date to include all data.

Note: participants who did not receive a second vaccination will not have a Post-dose 2 or Follow-up 2 period.

The periods/phases will be used primarily for allocation of adverse events to various time periods during the study. Adverse events will be summarized for each of the active periods, 'Post-dose 1' and 'Post-dose 2', as well as Post-dose 1 and Post-dose 2 Combined, which is referred to as

‘Regimen’. Additionally, for SAEs and AEs leading to discontinuation of study vaccine tables, an ‘Entire study’ period will be defined. ‘Entire study’ covers the time window from vaccination 1 up to and including the end of the study for each participant.

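### Laboratory and vital-sign abnormalities that were already present before the Day 57 injection count again as emerging in Post-dose 2, because the only reference is the pre-Day-1 baseline

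*SAP*

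**What the plan says.** SAP 5.1.1 sets one reference: "A baseline (or reference) value will be defined as the value of the last available assessment prior to the vaccination on Day 1". It also states: "The safety analysis will present all results by phase". SAP 5.6.2 says that an abnormality "will be considered as emerging in a particular period if it is worse than the baseline value", and adds: "Worst grades/abnormalities are determined over the whole observational period for each trial period separately, including all post-baseline measurements of that period". It also says: "If the baseline is missing, the abnormality is always considered emerging".

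In the SAP phase-definition table, Post-dose 2 opens at "Date and time of second vaccination". Day 57 pre-dose values therefore fall in Follow-up 1.

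The Schedule of Activities (Protocol 1.3.1) takes haematology and chemistry pre-dose on Day 57 and again on Day 64, which is the only scheduled laboratory sample in Post-dose 2. Vital signs are taken before and after the Day 57 injection, then on Days 64 and 85. A note in Protocol 5.2 says: "The clinical laboratory results on Day 1 and Day 57 are not required for eligibility assessment".

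Protocol 4.2 says that high-dose vaccine "administered in a 2-dose or single-dose regimen will be assessed". In the study design table, Groups 6 and 7 (25 each) receive active vaccine on Day 1 and placebo on Day 57.

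Unsolicited adverse events follow a different rule: SAP 5.6.1.3 assigns them to the period in which they start.

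**The concern.** A table headed Post-dose 2 invites the reader to see what appeared after the second injection. Under this rule it also contains what was already there just before that injection, provided it was absent or milder at the Day 1 baseline. The value needed to tell the two apart is collected at the Day 57 visit, but the SAP never uses it as a reference.

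The laboratory and adverse-event tables therefore answer different questions. An adverse event that began in Follow-up 1 and continues is not newly allocated to Post-dose 2; a persisting laboratory abnormality is. At stake is the by-dose reading of the tables, most plainly in Groups 6 and 7, where a lasting effect of the active first dose would appear in the period after a placebo injection. SAP 5.8 makes safety one of the inputs to regimen selection.

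**Working it through.** The plan states no figure for this rule, so there is none to reproduce. The check is of the logic, followed by an illustration of size.

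**1. Grade patterns.** Let b be the grade at the Day 1 baseline, p the grade pre-dose on Day 57, and w the worst grade in Post-dose 2. The SAP rule is w > b. The stricter rule is w > b and w > p.

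| b | p | w | SAP rule | Worse than both |
|---|---|---|---|---|
| 0 | 2 | 2 | emerging | no |
| 0 | 2 | 1 | emerging | no |
| 2 | 2 | 2 | no | no |
| 0 | 0 | 2 | emerging | yes |

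**2. All patterns.** With grades 0 to 4 there are 5 × 5 × 5 = 125 combinations.
- Flagged by the SAP rule: 10 pairs with w > b, times 5 values of p = 50.
- Flagged, but no worse than Day 57 pre-dose (p ≥ w): for w = 1, 2, 3, 4 this gives 1×4 + 2×3 + 3×2 + 4×1 = 20. In 10 of these the value equals the pre-dose grade and in 10 it has improved.
- Flagged under both references: 50 − 20 = 30.

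These are counts of logical patterns, not expected rates.

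**3. Illustrative size.** The documents give no persistence rate. Assume that a proportion q of participants has an abnormality that arose after the baseline and persists from Day 57 pre-dose to Day 64, and that Dose 2 has no effect. The expected count in a group of 25 is 25q, the expected count in Groups 6 and 7 together is 50q, and the chance of at least one case in 25 is 1 − (1 − q)^25.

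| q (assumed) | Expected in 25 | Expected in Groups 6+7 (50) | Chance of at least one in 25 |
|---|---|---|---|
| 2% | 0.5 | 1 | 40% |
| 5% | 1.25 | 2.5 | 72% |
| 10% | 2.5 | 5 | 93% |
| 20% | 5 | 10 | above 99% |

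Each carried-over case is 1/25 = 4 percentage points.

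**4. Single- versus two-dose contrast.** Groups 4 and 6 share a first dose, as do Groups 5 and 7, so the expected carry-over q is the same within each pair. If an active Dose 2 independently adds new abnormalities with probability d, and placebo adds none, the Post-dose 2 rates are q + (1 − q)d and q. The difference is (1 − q)d. For q from 2% to 20% this is 98% to 80% of d: attenuated, with the sign unchanged.

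**5. Comparison with all-placebo groups.** Groups 3 and 8 (10 + 10 = 20 participants) have no active first dose. Their carry-over reflects background change only, while that of an active group also includes any lasting effect of Dose 1. The two do not cancel.

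**The case against.** Being worse than before any study vaccination is a coherent definition, and it matches how SAP 5.3.3 treats emergent adverse events. It over-counts rather than misses, which is the cautious direction in a first-in-human study. Clinically relevant laboratory changes are also recorded as adverse events (Protocol 8.2.3), and unsolicited adverse events are allocated by start date. Listings by phase and time point let a reader trace carry-over, and vital signs are also summarised over time. Laboratory and vital-sign grades are not among the primary endpoints. All of this stands, and it is why the existing table should stay. It does not give the reader a Post-dose 2 summary that separates new from persisting abnormalities.

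A reader might go further and infer four things that the documents do not support.
- *That the SAP attributes these abnormalities to Dose 2.* It tabulates them in a period, descriptively and without a causal statement.
- *That anything abnormal before Day 57 is counted.* An abnormality at the same grade at baseline is not, unless the baseline is missing.
- *That the randomised single- versus two-dose comparison is biased.* Step 4 shows dilution only.
- *That all 70 recipients of a Day 57 placebo are affected by carry-over from an active dose.* Twenty of them never receive active vaccine; the active-then-placebo groups hold 50.

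Whether these data could also be listed under placebo as a vaccine is conditional. SAP 5.6 leaves the choice of by-vaccine tables to the Data Presentation Specifications. If they are included, 50 of the 90 planned placebo injections (20 × 2 + 50) follow an active first dose. Those specifications are not available here, so a shift table may already be planned in them; the SAP does not specify one.

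**Conclusion.** The point holds as a limitation of the by-period tables. SAP 5.1.1, the phase definitions and SAP 5.6.2 together count a persisting, or even improving, post-baseline abnormality as emerging in Post-dose 2. This inflates Post-dose 2 counts within groups and their comparison with the all-placebo groups.

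The size cannot be taken from the documents. The range of 0.5 to 5 participants per group of 25 rests wholly on the assumed 2-20% persistence. Participants are screened as healthy, and graded values within local normal limits are treated as normal, so the true figure could lie at or below the low end. The dilution result assumes that Dose 2 acts independently of carry-over. The present tables remain valid if read as worse than before the study.

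**What to change.** Keep the table referenced to the Day 1 baseline. In SAP 5.6.2, for participants who receive a second injection, add for Post-dose 2:

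- a tabulation of abnormalities worse than both the Day 1 baseline and the last value before Dose 2, using the Day 1 baseline alone if the pre-Dose-2 value is missing;
- a shift table from the last value before Dose 2 to the worst Post-dose 2 value.

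A footnote to the existing Post-dose 2 table should say that it includes abnormalities present before the second injection.

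The cost is a short SAP addition and two outputs from data already collected. The added tabulation has its own blind spots: it will not show an abnormality that began before Dose 2 and was only prolonged by it, and one aberrant Day 57 reading could hide a real change. It should therefore supplement the existing table, not replace it.

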## 5.7. Other Analyses

### 5.7.1. Immunogenicity

The analysis of immunogenicity will use the PPI set. A sensitivity analysis excluding additional samples after suspected sub-clinical influenza infection might be performed.

Data will be presented by the vaccine group (placebo from Cohort 1 and 2 will be combined) and by the scheduled time point. For the PPI analysis, samples taken outside of the allowed window will be excluded from the tables and graphs (but will be included in the listings and clearly marked as results not included in the PPI analyses).

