In Cohort 2, 110 participants aged ≥ 18 to ≤ 45 years will be enrolled in a staggered approach with safety evaluations in place before extending enrollment in this cohort. Initially, 5 sentinel participants will be enrolled and randomized; 1 participant in each of the 5 groups (Groups 4 to 8 [including 1 placebo]) will receive a single IM injection of either CCI [REDACTED] INFLUENZA G1 mHA; CCI [REDACTED] INFLUENZA G1 mHA adjuvanted with Al(OH)₃; or placebo on Day 1. Sentinel participants will be contacted by telephone 48 hours post-vaccination to collect safety information. The blinded 48-hour post-vaccination safety data in these 5 sentinel participants will be reviewed by the PIs and SRP. Randomization of additional participants will be paused until this 48-hour sentinel safety evaluation is completed.

In the absence of any clinically significant findings, upon decision by PI(s) and SRP, an additional 10 participants will be enrolled and randomized in parallel (2 additional participants in Groups 4 to 8 [including 2 placebo]) as safety ramp-up subset .

DRC will review blinded safety data of the 15 participants in Cohort 2, 7 days after the first vaccination. DRC review will be held to review available safety data of initial participants enrolled before these participants can receive the second vaccination. Further randomization in Cohort 2 will be paused until the DRC safety evaluation is completed. In the absence of findings from the DRC following the first vaccination, the remaining 95 participants in Cohort 2 will be enrolled in a 22:22:22:22:7 ratio.

Second-dose Safety

In alignment with the first-dose safety strategy, post-second dose 48-hour (sentinel participants) and 7-day safety assessments (participants in the sentinel subset and safety ramp-up subset) will be monitored by the

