Blood and urine samples for clinical laboratory assessments will be collected as indicated in Section 1.3 Schedule of Activities and Section 10.6, Appendix 6: Clinical Laboratory Tests.

Blood will be collected from all participants to assess humoral immune responses pre-vaccination on each dosing day, at 7 days and at 28 days after each dose, at 6 months after the second dose, and at 12 months after the first dose (or at the early exit visit if the participant prematurely terminates the study without withdrawing consent ^a).

Participants should record signs and symptoms of influenza during the influenza season using a specific Influenza Intensity and Impact Questionnaire (Flu-iiQTM) and an ILI form. Participants will be informed of the timing of the start and end of the influenza season in accordance with the country/region-specific influenza local surveillance system. Procedures for Flu-iiQTM questionnaire and ILI form completion are described in Section 8.1.1, ILI Procedures. The Flu-iiQTM questionnaire and ILI form will be the primary source for influenza monitoring. Participants will be contacted by telephone or other means of communication every 14±3 days (unless a planned clinic visit has occurred or will occur within 14 days). Calls will remind the participants to complete the Flu-iiQTM questionnaire and ILI form in the event of any symptoms of influenza infection, to contact the site at the time of symptom onset, and to take a nasal swab at home preferably on the day of symptom onset or the day thereafter (ILI Days 1-2). Calls will also check for any SAEs and associated concomitant medications since the previous visit or telephone contact.

Full details of ILI procedures, including the collection of nasal swabs are provided in Section 8.1.1, ILI Procedures.

The presence of influenza virus infection will be assessed by qualified site staff by RT-PCR diagnostics and/or rapid-PCR detection (eg, by Cepheid GeneXpert[®]) on the nasal swab samples.

Seasonal Influenza Vaccination

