## 2. STATISTICAL HYPOTHESES

No formal statistical hypothesis on safety is to be tested. The study will evaluate whether INFLUENZA G1 mHA, with or without Al(OH)3 adjuvant, is safe, well tolerated, and immunogenic in healthy adults aged  $\geq 18$  to  $\leq 45$  years.

Safety data will be analyzed descriptively per vaccine group (placebo from Cohort 1 and 2 will be combined), with special attention to SAEs, Grade 3/4 AEs, and AEs leading to discontinuation of study vaccine.

No formal hypothesis on immunogenicity will be tested. Immunogenicity data will be analyzed descriptively per study group. Descriptive statistics (geometric mean and 95% CI, or median and quartile range [Q1-Q3], as appropriate) will be calculated for continuous immunological parameters at all time points and for changes from baseline.

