### 5.7.1.5. Immunogenicity

#### 5.7.1.5.1. Humoral assays

For ELISAs (H5-ELISA and mini-HA ELISA) and VNA the following results will be calculated: N, geometric mean§ and corresponding 95% CI of the actual values, and fold increases from baseline will be tabulated and graphically presented. *§calculate the mean and corresponding 95% CI of log10 transformed values, back-transform this mean [i.e., 10mean] and CI [i.e., 10CI].*

A sample is considered positive if the value is above the assay LLOQ.

A response will be defined as:

- if sample interpretation is negative at baseline and there is >4-fold increase from LLOQ (on the original scale), or,
- if sample interpretation is positive at baseline and there is a >4-fold increase from baseline (on the original scale).

Tables will show the sample positivity, responders, and the percentage of participants with a >2-fold increase.

Geometric mean ratios (GMR) § between active groups and placebo group (pooled across cohort 1 and 2), with corresponding 95% CIs will be estimated via an analysis of variance (ANOVA), using log-transformed post-baseline value as dependent variable and study group as independent variable. As a sensitivity analysis, the ANOVA may also be performed adjusting for the respective baseline titers, by including log-transformed baseline titer as additional covariate. *§by back-transform LSmean and corresponding 95% CI from ANOVA [i.e., 10LSmean] and CI [i.e., 10CI].*

Actual values and fold changes from baseline are tabulated and shown as dot plots with dots for participant values, and the corresponding geometric mean and 95% CI per time point for each assay.

In the graphs, original values will be displayed on the log10 scale. The actual values will be shown, even if they are below the LLOQ. The LLOQ cut-off will be visualized in the graph per assay. Participant profiles of the actual values over time will also be graphically presented. A correlation plot of H5 ELISA versus mini-HA ELISA will be provided for the most important time points (at minimum, Baseline, Day 29, and fold increase from Baseline at Day 29).

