### **Extended Breadth Score**

The analysis of extended breadth score will be performed on a subset of participants from the PPI analysis set who have samples for analysis at both Day 1 and Day 29.

A random selection of about 75 participants in total from three FLZ1001 study groups and 76 participants from SF-SC cohort from VAC31518COV3005 study (see section 5.7.1.6.1) will be made. For FLZ1001, all participants meeting criteria from the INFLUENZA G1 mHA CCI - INFLUENZA G1 mHA CCI group will be included in the subset. A random sample of 30 participants from the pooled group of INFLUENZA G1 mHA CCI - INFLUENZA G1 mHA CCI and INFLUENZA G1 mHA CCI - placebo groups and from the pooled group of INFLUENZA G1 mHA CCI Al(OH)3 - INFLUENZA G1 mHA CCI Al(OH)3 and INFLUENZA G1 mHA CCI Al(OH)3 - placebo groups will be made respectively. Selecting 30 subjects will allow for a total of 25 subjects to be included in the subset from each of those two groups, where subjects with vials with low volume are excluded.

The same three types of breadth scores (Narrow H1 score, Broad Group 1 score, and Group 1 score excluding H1) will be calculated based on the extended breadth panel assays (as identified in Table 5) using Maximum Diversity Weighting method. The ELISAs that were included in the original breadth scores are also included in the extended breadth scores for selected subjects. The extended breadth scores will include additional ELISAs as detailed below:

- Narrow H1 score (H1 strains as identified in Table 5):
  - o The same ELISAs that are included in the Narrow H1 score.
  - o In addition, the mini-HA ELISA (A/New Caledonia/20/1999) is included.
- Broad Group 1 score (Group 1 strains as identified in Table 5):
  - o The same ELISAs that are included in the Broad Group 1 score.
  - o In addition, the following ELISAs are included: mini-HA (A/New Caledonia/20/1999); H5 (A/Cambodia/NPH230032/2023); H2 (A/avian/Japan/KU-d3c/2020); and H9 (A/Cambodia/21020301/2021).
- Group 1 score excluding H1 (Group 1 strains as identified in Table 5):
  - o The same ELISAs that are included in the Group 1 score excluding H1.
  - o In addition, the following ELISAs are included: H5 (A/Cambodia/NPH230032/2023); H2 (A/avian/Japan/KU-d3c/2020); and H9 (A/Cambodia/21020301/2021)

Analysis will be done in a similar way as described above for the Breadth score.

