## **Extended Breadth Coverage**

Same as for extended breadth scores, Extended Breadth Coverage was calculated using additional extended breadth panel. Results are presented in a similar way as described above for the Breadth coverage.

**Nasal antibody response** may be assessed using IgA and/or IgG ELISA in nasal secretions and presented in a similar way as described above for the core ELISAs and VNA. Nasal antibody response will be done on the same subject selection as for extended breadth ELISA panel for the FLZ1001 study only at Day 1 and Day 29. Two different types of nasal swab are used in the study, namely nylon flock and SAM. Attempt to normalize values reported by two different swab types will be made to be able to pool results in same summary table. If normalization will not be successful, the data will instead be summarized by swab type.

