### 5.7.1.6.2. Humoral assays

Descriptive statistics and graphs on humoral immunogenicity data listed in [Table 4](#) (where available) will be done similarly as described in section [5.7.1.5.1.](#) for the COV3005 Broad SF-SC cohort (H5 ELISA, mini-HA ELISA, VNA, Human Fc $\gamma$ RIIIa reporter assay, breadth ELISAs including three breadth scores, coverage score, and HAI assay) and for the SF-SC cohort.

For H5 ELISA, mini-HA ELISA, VNA, Human Fc $\gamma$ RIIIa reporter assay, and three breadth scores, geometric mean ratios (GMR)  $\ddagger$  between active groups (FLZ1001 vs. SF-SC cohort), with corresponding 95% CIs will be estimated via an analysis of variance (ANOVA), using log-transformed 28 days post-dose 1 immune parameter response as dependent variable and study group as independent variable. As a sensitivity analysis, the ANOVA may also be performed adjusting for the respective baseline titers, by including log-transformed baseline titer as an additional covariate.  $\ddagger$ by back-transform LSmean and corresponding 95%CI from ANOVA [i.e.,  $10^{LSmean}$ ] and CI [i.e.,  $10^{CI}$ ].

In addition, GMR plots over time, combining the regimens in one graph (without individual participant dots) will also be created.

For the breadth coverage, least square mean differences between active groups (FLZ1001 vs. SF-SC cohort), with corresponding 95% CIs will be estimated via an analysis of variance (ANOVA), using 28 days post-dose 1 breadth coverage as dependent variable and study group as independent variable. As a sensitivity analysis, the ANOVA may also be performed adjusting for the respective baseline value, by including baseline breadth coverage as an additional covariate.

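### Before the second dose, the main immunogenicity analyses keep apart high-dose groups that have had identical treatment, and so lose precision

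*SAP*

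**What the plan says.** Protocol 4.1 (Table 1) and 4.2 describe Cohort 2 as the high dose, with and without Al(OH)3, given either twice or once. Groups 6 and 7 receive placebo on Day 57, where Groups 4 and 5 receive active vaccine. The dose values are redacted. That the first dose is the same within each pair follows from Protocol 4.2 and from the SAP's own pooling described below. The five Cohort 2 groups are enrolled side by side at every step. After the sentinel and ramp-up participants, the "remaining 95 participants in Cohort 2 will be enrolled in a 22:22:22:22:7 ratio". On sampling, Protocol 4.1 says: "Blood will be collected from all participants to assess humoral immune responses pre-vaccination on each dosing day". The Schedule of Activities marks the Day 57 serum sample as pre-dose.

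For immunogenicity, SAP 5.7.1 says: "Data will be presented by the vaccine group (placebo from Cohort 1 and 2 will be combined) and by the scheduled time point". SAP 2 says: "Immunogenicity data will be analyzed descriptively per study group". The model in SAP 5.7.1.5.1 for ratios to pooled placebo is an ANOVA "using log-transformed post-baseline value as dependent variable and study group as independent variable". Breadth scores and breadth coverage are modelled in the same way, and FcγRIIIa data are to be handled like the core assays. The comparison with the SF-SC cohort in SAP 5.7.1.6.2 is an ANOVA "using log-transformed 28 days post-dose 1 immune parameter response as dependent variable", again with study group as the factor.

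The Extended Breadth Score text differs. It plans: "A random selection of about 75 participants in total from three FLZ1001 study groups". These three are the low-dose group and the two high-dose pairs, each pair pooled before sampling. For the nasal assay: "Nasal antibody response will be done on the same subject selection as for extended breadth ELISA panel".

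Neither *vaccine group* nor *study group* is defined.

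**The concern.** Until the Day 57 injection a participant in Group 4 and one in Group 6 have received the same thing, under the same concurrent randomisation and blind. The same holds for Groups 5 and 7. At Day 8, Day 29 and Day 57 pre-dose, separate columns for the two members of a pair are two estimates of one quantity, each resting on half of the participants who inform it. They will differ by chance, and a reader could take that difference for a regimen effect before any second dose has been given.

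The visits affected matter. Day 29 is among the time points that SAP 5.7.1.5.1 singles out as most important for its correlation plots. The SF-SC comparison uses only the response 28 days after dose 1, which is exactly where the pairs are identical. The H5 and mini-HA ELISAs carry the secondary endpoint, and immunogenicity results feed the choice of regimen (Protocol 9.5, SAP 5.8).

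Low-dose, placebo, extended-breadth and nasal results are not affected.

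**Working it through.** **Inputs.** Protocol 9.2 gives 22 evaluable participants per regimen (25 less 12%), log10 SDs from 0.181 to 0.783, and two-sided alpha 0.05. A pooled pair has 2 × 22 = 44. Two sizes are assumed:
- Evaluable placebo: 18 (20 planned × 0.88 = 17.6), with a range of 16 to 20.
- SF-SC: 76, a size the SAP gives only for the extended panel, with a range of 50 to 200. The SF-SC is drawn from a broader set of 200.

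**The plan's own figures.** Protocol Table 5 reproduces as a two-sample t-test on the log10 scale with 22 per group. For a 1.5-fold difference at SD 0.301 it gives 47.5% (stated 47.4%), and for 2-fold at SD 0.421 it gives 63.9% (stated 63.9%). All non-null cells agree within 0.2 points. So 22 per group and these SDs are the right basis.

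**1. Geometric mean titre of one arm.** The half-width on the log10 scale is t(0.975, n−1) × SD/√n. Going from n = 22 to n = 44 multiplies it by 0.686, a 31% reduction. Back-transformed:

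| SD (log10) | n = 22 | n = 44 |
|---|---|---|
| 0.301 | ×/÷1.36 | ×/÷1.23 |
| 0.421 | ×/÷1.54 | ×/÷1.34 |
| 0.542 | ×/÷1.74 | ×/÷1.46 |

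**2. Ratio to pooled placebo.** The SE is SD × √(1/n₁ + 1/n₂).
- By regimen: √(1/22 + 1/18) = 0.3178.
- By Day 1 vaccine: √(1/44 + 1/18) = 0.2798.
- Reduction: 12.0% (11.1% with 16 placebo, 12.7% with 20).
- At SD 0.421, in a one-factor ANOVA with 6 × 22 + 18 = 150 evaluable participants (143 error df by regimen, 145 by Day 1 vaccine), the interval goes from ×/÷1.84 to ×/÷1.71.

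**3. Ratio to SF-SC at 28 days after dose 1.**
- By regimen: √(1/22 + 1/76) = 0.2421.
- By Day 1 vaccine: √(1/44 + 1/76) = 0.1894.
- Reduction: 21.8% (19.2% at n = 50, 25.9% at n = 200).
- At SD 0.421 the interval goes from ×/÷1.59 to ×/÷1.44.

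The percentage reductions in SE depend only on the sample sizes, so they also apply to breadth coverage, which is analysed as means rather than ratios. The back-transformed factors do not.

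**4. Chance spread within a pair.** The SE of the difference between two separate log10 means of the same treatment is SD × √(2/22) = SD × 0.3015. The probability of a difference greater than k-fold is 2 × [1 − Φ(log10 k / (0.3015 × SD))].

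| Difference exceeds | SD 0.301 | SD 0.421 | SD 0.542 |
|---|---|---|---|
| 1.25-fold | 29% | 45% | 55% |
| 1.5-fold | 5% | 17% | 28% |

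The 1.25-fold mark is illustrative and does not come from the documents. The 1.5-fold mark is the smallest non-null difference in Protocol Table 5.

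**The case against.** The strongest reply is that the SAP does not rule pooling out. The group terms are undefined, the one place that counts study groups counts pooled pairs, and the table shells sit in the Data Presentation Specifications, which are not among the documents. That is fair as far as it goes: separate analysis is the natural reading of the main SAP text, not the only one. But the SAP is where the methods are set, and it names placebo alone as combined. Where it wants a display per injection it says so, as in the by-vaccine safety layout of SAP 5.6. Immunogenicity has no counterpart.

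Second, analysis by randomised regimen is valid, matches the aim of selecting a regimen, and gives stable columns out to Day 365. No hypothesis is tested. This stands, and it is why the by-regimen columns should stay. It is not a reason to leave out the better estimate of the first-dose response.

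Third, the pooling in the extended-breadth text is stated at the sampling step and yields 25 per arm, the size of one planned group, so it does not itself deliver the precision of 44. This is also true. What that text shows is that the SAP treats each pair as interchangeable after dose 1.

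Fourth, the gain is modest where it counts. Against placebo it is about 12%, because the placebo arm is small. The ANOVA already draws its error variance from all groups, so only the mean, not the variance estimate, rests on half the data. A reader could also approximate a pooled mean from the tabulated figures. Day 29 ratios cannot separate one dose from two, and no decision threshold is given that the tighter intervals would cross. These points bound the size of the problem but do not remove it.

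**Conclusion.** The concern holds. As written, the SAP reports the high-dose first-dose response, with and without adjuvant, as two half-size estimates each at Day 8, Day 29 and Day 57 pre-dose. This is a loss of precision, not a bias, and the by-regimen results remain valid.

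The loss is largest for single-arm geometric means, smaller against SF-SC and smallest against placebo. It rests on 22 evaluable participants per regimen, a common SD within the range in Protocol 9.2, and the assumed 18 placebo and 76 SF-SC participants. An adjuvanted versus unadjuvanted comparison would gain more (SE 29% smaller, √(2/44) against √(2/22)), but the SAP does not plan one. The remaining uncertainty is whether the unseen table specifications already contain pooled columns. Even then the SAP would need to define its group terms and say which estimate describes the first-dose response.

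**What to change.** - In SAP 5.7.1, define *vaccine group* and *study group*.
- In SAP 5.7.1.5.1, for Day 8, Day 29 and Day 57 (pre-dose 2), add geometric means, fold rises and ratios to pooled placebo by Day 1 vaccine, with Groups 4 and 6 pooled and Groups 5 and 7 pooled. For breadth coverage add the corresponding means and mean differences.
- In SAP 5.7.1.6.2, add the ratios (for breadth coverage, the mean differences) to SF-SC at Day 29 on the same pooled basis.
- State in advance that these pooled figures are the estimates of the first-dose response.
- Keep the by-regimen columns at the early visits so that each regimen can be followed from baseline. From Day 64, where the pairs have diverged, present by regimen only.

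The cost is wording in the SAP and the table specifications, and two extra columns in each Day 8 to Day 57 table. The drawback is a second set of early estimates, which is why the SAP must say which set answers which question.
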